3.3.5 Rationale for Other Study Design Elements

3.3.5.1 Efficacy Measurements

The American College of Rheumatology (ACR) response criteria are commonly used in RA studies and accepted by health authorities to measure reduction in RA disease activity; ACR50 has been chosen as the primary efficacy endpoint because it measures a more robust response with a lower placebo response rate than ACR20, which has traditionally been used by most pivotal trials in RA. In addition, several other clinically meaningful aspects of RA will be evaluated, including Disease Activity Score (DAS) 28 remission and low disease activity, Boolean remission, Simplified Disease Activity Index (SDAI), Clinical Disease Activity Index (CDAI), and patient-reported outcome (PRO) measures (i.e., Health Assessment Questionnaire—Disability Index [HAQ-DI], Short-Form 36 Health Survey [SF-36] v2, and Functional Assessment of Chronic Illness Therapy [FACIT]-Fatigue Scale [see Appendix 5, Appendix 6, and Appendix 7, respectively]). Each of these measures has been well established and validated in previous studies. The kinetics of response to GDC-0853 will be carefully evaluated throughout the course of this study at regular intervals.

Efficacy based on SJC and TJC will be assessed at Weeks 12 and 24, and improvement will be calculated using formulas provided in Appendix 9. If a 20% improvement in SJC and TJC (relative to baseline values in the blinded Study GA29350) is not observed by Week 12, concomitant therapy will be escalated (e.g., adjusting the dose of corticosteroids, MTX, or both as well as the possible addition or substitution of other DMARDs; see Section 4.3.1.1.3). If a 20% improvement in SJC and TJC (relative to baseline values in the blinded Study GA29350) is not observed by Week 24, the patient will be discontinued from this study because of lack of efficacy. Confirmation of efficacy at these prescribed intervals will help to ensure that patients are not kept on an ineffective treatment for a prolonged period of time.

3.3.5.2 Clinical Outcomes Assessments

PRO and clinician-reported outcome (ClinRO) data will be collected to more fully characterize the clinical profile of GDC-0853. To minimize the confounding of PRO assessments that evaluate pain, any potentially painful procedures (e.g., blood draws) should be performed after the pain assessment. In cases where this is logistically challenging, potentially painful procedures will be performed at least 15 minutes prior to initiation of the PRO measures.

3.3.5.3 Concomitant Medications

Patients in this study will be able to continue on their background MTX therapy, because this represents a common treatment paradigm for patients who initiate additional therapies following an inadequate response to MTX and/or TNF inhibitors. Stability of MTX and other concomitant medications will be encouraged for the first 12 weeks of this study, in order to assess efficacy at Week 12, which represents a total of 24 weeks of treatment for a proportion of patients coming from the blinded Study GA29350. In addition, there will be more flexibility in the dosing of specified concomitant DMARDs and corticosteroids after Week 12 to optimize patient care, which will also enable a better understanding of the long-term safety and efficacy of GDC-0853 in a real-world context.

4. MATERIALS AND METHODS

4.1 PATIENTS

Up to 580 patients from Study GA29350 will be enrolled in this study.

4.1.1 Inclusion Criteria

Patients must meet the following criteria for study entry:

- Age 18 to 76 years
- Able and willing to provide written informed consent and to comply with the requirements of the protocol
- Completion of treatment period through Day 84 as specified in Study GA29350
- Acceptable safety and tolerability during Study GA29350 as determined by the investigator or Medical Monitor
- Have not received any prohibited medications in Study GA29350
- While taking MTX, must be willing to receive oral folic acid (at least 5 mg/week)
- If receiving oral corticosteroids (≤10 mg/day prednisone or equivalent) and/or NSAIDs (up to the maximum recommended dose), doses have remained stable for the duration (i.e., since the first administration of study drug) of Study GA29350. If a change in dose was needed during Study GA29350, discuss with the Medical Monitor.
- Women of childbearing potential must test negative for pregnancy prior to enrollment

For women of childbearing potential (including those who have had a tubal ligation):
 Agreement to remain abstinent (refrain from heterosexual intercourse) or use
 contraceptive methods that result in a failure rate of <1% per year during the
 treatment period and for at least 60 days after the last dose of study drug (see
 Appendix 4)

A woman is considered to be of childbearing potential if she is postmenarcheal, has not reached a postmenopausal state (≥ 12 continuous months of amenorrhea with no identified cause other than menopause), and has not undergone surgical sterilization (removal of ovaries and/or uterus).

Examples of contraceptive methods with a failure rate of <1% per year include bilateral tubal ligation, male sterilization, established proper use of hormonal contraceptives that inhibit ovulation, hormone-releasing intrauterine devices, and copper intrauterine devices. Women using estrogen-containing hormonal contraceptives as a method of contraception must also use a barrier, such as a male condom, in conjunction with the hormonal contraceptives.

The reliability of sexual abstinence should be evaluated in relation to the duration of the clinical trial and the preferred and usual lifestyle of the patient. Periodic abstinence (e.g., calendar, ovulation, symptothermal, or post-ovulation methods) and withdrawal are not acceptable methods of contraception.

 For men: Agreement to remain abstinent (refrain from heterosexual intercourse) or use contraceptive measures, and agreement to refrain from donating sperm, as defined below (also see Appendix 4)

Men with female partners of childbearing potential (including those who have had a tubal ligation) must remain abstinent or use a condom plus an additional contraceptive method that together result in a failure rate of <1% per year during the treatment period and for at least 120 days (4 months) after the last dose of study treatment. Men must refrain from donating sperm during this same period.

Men with pregnant female partners must remain abstinent or use a condom during the treatment period and for at least 28 days after the last dose of study treatment to avoid exposing the fetus.

The reliability of sexual abstinence should be evaluated in relation to the duration of the clinical trial and the preferred and usual lifestyle of the patient. Periodic abstinence (e.g., calendar, ovulation, symptothermal, or post-ovulation methods) and withdrawal are not acceptable methods of contraception.

4.1.2 Exclusion Criteria

Patients who meet any of the following criteria will be excluded from study entry:

- Met protocol-defined treatment-stopping criteria during Study GA29350
- Treatment with any investigational agent (i.e., other than study drug) or live/attenuated vaccine during Study GA29350 or since the last administration of study drug in Study GA29350

 Treatment with any of the following prohibited medications during Study GA29350 or since the last administration of study drug in Study GA29350:

TNF inhibitors (except adalimumab for patients from Cohort 1), anti-IL-6 or anti-IL-6 receptor antagonists, anti-CD20, abatacept, anakinra, all biosimilar agents

JAK inhibitors

Azathioprine, chlorambucil, cyclophosphamide, cyclosporine, gold, immunosorbent column, mycophenolate mofetil, mycophenolic acid sodium, penicillamine, sirolimus, tacrolimus

Oral anticoagulants (including but not limited to warfarin, dabigatran, rivoxaban, apixaban), anti-platelet agents (e.g., clopidogrel; note: NSAIDs and aspirin of 162 mg/day or less are acceptable), heparin, low-molecular-weight heparin (LMWH)

- In the opinion of the investigator, any new (since initially enrolling in the Phase II Study GA29350), significant, uncontrolled comorbidity, such as neurological, cardiac (e.g., moderate to severe heart failure New York Heart Association Class III/IV), pulmonary, renal, hepatic, endocrine, or GI disorders (excluding RA) that would increase the risk to the patient in Study GA30067
- Pregnant or lactating or intending to become pregnant during the study
- Any uncontrolled or clinically significant laboratory abnormality that would affect safety, interpretation of study data, or the patient's participation in the study in the opinion of the investigator
- Patients who experienced a de novo or reactivated serious viral infection such as hepatitis B virus, hepatitis C virus, or HIV during the Phase II Study GA29350
- Any major episode of infection requiring hospitalization or treatment with IV antibiotics during the Phase II Study GA29350
- Patients who developed a malignancy (with the exception of non-serious local and resectable basal or squamous cell carcinoma of the skin) during the Phase II Study GA29350
- 12-lead ECG on Day 84 in Study GA29350 that demonstrates clinically relevant abnormalities that may affect patient safety or interpretation of study results, including

QT interval corrected using Fridericia's formula (QTcF) > 440 msec demonstrated by at least two ECGs > 30 minutes apart

- Current treatment with medications that are well known to prolong the QT interval
- Laboratory values from the Day 56 visit of Study GA29350 (which may be repeated once at an unscheduled visit, if necessary) that meet the following criteria:

Creatinine > 1.5 × ULN

ALT or AST > 1.5 × ULN

Total bilirubin > ULN

Hemoglobin < 8.5 g/dLANC $< 1.5 \times 10^9 \text{/L}$ Platelet count $< 100 \times 10^9 \text{/L}$

4.2 STUDY TREATMENT

The investigational medicinal product (IMP) for this study is GDC-0853.

4.2.1 Formulation, Packaging, and Handling

GDC-0853 will be provided by the Sponsor as 50-mg dose strength tablets.

Tablets will be supplied in bottles, which will be appropriately labeled for this study. GDC-0853 tablets should be stored *between* 2 °C and 8 °C.

For information on the formulation and handling of GDC-0853, see the GDC-0853 Investigator's Brochure and pharmacy manual.

4.2.2 Dosage, Administration, and Compliance

4.2.2.1 GDC-0853 Dose and Administration

The GDC-0853 dose regimen is oral 200 mg BID. Patients will receive GDC-0853 approximately every 12 hours for 52 weeks. Patients should be directed to take one dose (a total of 4 tablets) BID (total of 8 tablets each day). On clinic visit days during the first 12 weeks of the study, patients should be instructed that the a.m. dose of GDC-0853 will be administered in the clinic, except for Day 1, since the last dose of GDC-0853 for Study GA29350 is the a.m. dose on Day 84 for all patients. For patients continuing into the OLE Study GA30067, the first open-label dose of GDC-0853 should be the p.m. dose (may be taken at home) on Day 84 (which is Day 1 of Study GA30067). After Week 12, GDC-0853 administration in the clinic is not required.

A dose reduction of GDC-0853 for specific safety events is permitted (see Table 3). For a potential dose reduction for other adverse events not listed in the table, please consult the Medical Monitor. If dose reduction is indicated, the dose of GDC-0853 may be reduced from 200 mg BID to 200 mg QD. In this case, patients should be directed to take one dose (a total of 4 tablets) QD in the morning (total of 4 tablets each day).

Guidelines for dose reduction and treatment interruption or discontinuation are provided in Section 5.1.

GDC-0853 may be orally administered with or without food. The dates and times of the most recent prior meal, last dose of GDC-0853 (prior to clinic visit), and timing of GDC-0853 administration in clinic should be recorded at each clinic visit. In addition, any use of PPIs, H2-receptor antagonists (H2RAs), and/or other antacids (e.g., Maalox®, Pepto-Bismol®, Rolaids®) should be recorded as concomitant medications, including time and date of last administration. Administration of GDC-0853 should be staggered with antacid use (i.e., GDC-0853 should be taken 2 hours before or 2 hours after the antacid).

GDC-0853—Genentech, Inc. 51/Protocol GA30067, Version 2

At study visits, sufficient GDC-0853 tablets will be dispensed to complete dosing until the next scheduled visit. When GDC-0853 is administered at the site, it will be administered under supervision of study personnel, and the amount of GDC-0853 dispensed must be recorded.

4.2.2.2 *GDC-0853 Compliance*

The following measure will be taken to assess patient compliance with study drug: patients will be directed to bring any used and unused bottles to each visit.

Sites will be responsible for prepopulating the dates on the dosing label (that should be affixed to the bottle) for when patients are scheduled to take study drug. Under the corresponding dates listed, the patients will record the times (a.m. or p.m.) that they take each dose on the affixed label. (Refer to Appendix 10 for the bottle and label configuration.) The number of tablets issued minus the number of tablets returned will be used to calculate the number of tablets taken and compliance.

Compliance will be documented on the source record.

Any overdose or incorrect administration of study drug should be noted on the Study Drug Administration electronic Case Report Form (eCRF). Adverse events associated with an overdose or incorrect administration of study drug should be recorded on the Adverse Event eCRF. If compliance is $\leq 80\%$, the investigator or designee is to counsel the patient and ensure steps are taken to improve compliance.

4.2.3 Investigational Medicinal Product Accountability

The IMP required for completion of this study (GDC-0853 tablet) will be provided by the Sponsor. The study site will acknowledge receipt of the IMP using the Interactive Voice/Web Response System (IxRS) to confirm the shipment condition and content. Any damaged shipments will be replaced.

The IMP will either be disposed of at the study site according to the study site's institutional standard operating procedure or returned to the Sponsor with the appropriate documentation. The site's method of IMP destruction must be agreed to by the Sponsor. The site must obtain written authorization from the Sponsor before any IMP is destroyed, and IMP destruction must be documented on the appropriate form.

Accurate records of all IMPs received at, dispensed from, returned to, and disposed of by the study site should be recorded on the Drug Inventory Log.

4.2.4 Post-Trial Access to GDC-0853

Currently, the Sponsor (Genentech, a member of the Roche Group) does not have any plans to provide GDC-0853 or any other study treatments or interventions to patients who have completed Study GA30067. The Sponsor may evaluate whether to continue

providing GDC-0853 in accordance with the Roche Global Policy on Continued Access to Investigational Medicinal Product, available at the following Web site:

http://www.roche.com/policy_continued_access_to_investigational_medicines.pdf

4.3 CONCOMITANT THERAPY, PROHIBITED FOOD, AND ADDITIONAL RESTRICTIONS

Concomitant therapy includes any medication (e.g., prescription drugs, over-the-counter drugs, vaccines, herbal or homeopathic remedies, nutritional supplements) used by a patient from the start of the OLE Study GA30067 (Day 1) until the study completion visit. A patient who is receiving an allowed concomitant medication for any reason must be on a locally approved medication and dose that is considered standard of care for the treated indication. All concomitant medication taken during the study must be recorded with indication, daily dose, and start and stop dates of administration must be recorded on the appropriate pages of the eCRF. Adverse events related to the administration of a concomitant medication or the performance of a procedure must also be documented on the appropriate adverse event page of the eCRF.

If possible, it is recommended that patients avoid changing other prescription or non-prescription drugs, vitamins, and dietary supplements during the study.

4.3.1 Permitted Therapy

4.3.1.1 Use of Treatments for Rheumatoid Arthritis

The investigator must use the procedures outlined below in making modifications to these medications and document all changes in the eCRF. If necessary, unscheduled safety laboratory samples may be collected at the discretion of the investigator to monitor for toxicity from concomitant medications (e.g., DMARDs, NSAIDs, steroids).

4.3.1.1.1 Methotrexate

From the beginning of the study until Week 12, patients should continue to receive the same dose of MTX that they were receiving at the end of Study GA29350, which should be between 15 and 25 mg/week (doses as low as 7.5 mg/week are allowed only in the case of documented MTX intolerance). Dose reductions for MTX or a change of route of administration are allowed prior to Week 12 only for safety reasons. If dose reduction of MTX is a result of intolerance, such intolerance must be recorded as an adverse event and the dose modification must be recorded in the eCRF.

After Week 12, patients may change (i.e., increase, decrease, or discontinue) their dose of MTX and/or add other permitted DMARDs as clinically indicated and tolerated by the patient, according to the investigator's judgment (see Section 4.3.1.1.3).

4.3.1.1.2 Folic Acid

To prevent adverse events associated with MTX, patients are required to take folic acid or equivalent (e.g., 1 mg/day) at a stable dose of at least 5 mg/week (or equivalent)

while they are receiving MTX. This can be administered as either a single weekly dose or a daily dose per the discretion of the investigator.

4.3.1.1.3 Other DMARDs

At Week 12, if there has not been at least a 20% improvement in the SJC and TJC relative to the patient's baseline joint counts in the blinded Study GA29350, then therapy should be escalated per the investigator's judgment.

Starting at Week 12, concomitant DMARDs in addition to MTX that may be used during the study include hydroxychloroquine, chloroquine, sulfasalazine, and leflunomide, as clinically indicated and tolerated by the patient, according to the investigator's judgment. Allowable DMARDs can be used alone or in combination, except for the combination of MTX and leflunomide, which is not allowed. Dose reductions or discontinuations of DMARDs may be performed at any time for safety or for clinical improvement, per the investigator's judgment. If a dose reduction is a result of intolerance, such intolerance must be recorded as an adverse event and the dose modification must be recorded in the eCRF.

Treatment with certain medications, including but not limited to mycophenolate, calcineurin inhibitors, biologic agents (e.g., anti-TNF, anti-IL-6 or anti-IL6 receptor, anti-IL-1, T-cell costimulation modulator agents, anti-CD20), and JAK inhibitors (e.g., tofacitinib), is prohibited throughout this study (see Section 4.3.2).

4.3.1.1.4 Corticosteroids

Oral corticosteroids (\leq 10 mg/day) will be permitted during this study. If a patient was receiving background oral corticosteroids in Study GA29350, he or she should continue this same dose (\leq 10 mg/day prednisone or equivalent), which should remain stable for the first 12 weeks of the study. Starting at Week 12, corticosteroid doses may be modified (e.g., increased, tapered) on the basis of the investigator's clinical assessment of the patient. It is strongly encouraged that the dose not exceed 10 mg/day of prednisone or equivalent. Adjustment for safety reasons is allowed throughout the trial (see Section 4.3).

The use of IV or intramuscular corticosteroids is not permitted in this study.

Starting at Week 12 of this study, up to 3 intra-articular corticosteroid injections are permitted. No single injection should exceed 40 mg of triamcinolone or equivalent, and the total annual dose of intra-articular corticosteroid should not exceed 80 mg of triamcinolone or equivalent.

4.3.1.1.5 Non-Steroidal Anti-inflammatory Drugs

Patients may be treated with NSAIDs at up to the maximum recommended dose according to local labeling (including COX-2 inhibitors). Dose adjustments, including discontinuation, are permitted throughout the study. Dose adjustments may be made for

safety reasons at any time and if required to treat disease flares. If possible, dose adjustments should be avoided within 24 hours before a visit where clinical efficacy assessments are scheduled to be performed and recorded.

Topical NSAIDs are allowed.

Patients should receive NSAIDs only on an as needed (PRN) basis if absolutely required to treat RA disease flares, on the basis of the investigator's judgment; however, PRN use should be avoided within 24 hours before a visit where clinical efficacy assessments are scheduled to be performed and recorded.

Aspirin can be taken to reduce cardiovascular risk, but the dose is not to exceed 162 mg/day.

In order to prevent NSAID-related GI complications in high-risk patients, concomitant agents (e.g., PPIs) should be used according to local guidelines (see Section 5.1.1.3).

4.3.1.1.6 Analgesics (Other than NSAIDs)

Analgesics (e.g. acetaminophen, opioids) up to the maximum recommended doses may be used for pain as required. However, patients should not take analgesics within 24 hours prior to a visit where clinical efficacy assessments are to be performed and recorded. The total daily dose of acetaminophen may not exceed 2.6 g/day, and the total daily dose of opioid must not exceed the potency equivalent of 30 mg of orally administered morphine (see Appendix 2).

4.3.1.2 Dietary Supplements

For the purposes of this protocol, dietary supplements are defined as vitamins, minerals, purified food substances, and herbals with pharmaceutical properties.

Vitamins, minerals, and purified food substances are allowed in amounts not known to be associated with adverse effects (such as hypervitaminosis). Herbals with pharmaceutical properties are allowed only if there is acceptable evidence of no CYP3A inhibition or induction (refer to Appendix 3 for a list of prohibited concomitant medications, including herbal products). Otherwise, herbals with pharmaceutical properties must be discontinued for at least 4 weeks prior to first dose of study medication, unless there are sufficient data available regarding the duration of an herbal medication's PK and PD effects to allow a shorter washout to be specified (e.g., 5 half-lives). Please direct any questions to the Medical Monitor.

4.3.1.3 Acid-Reducing Agents

Patients who use antacids (e.g., Maalox[®], Pepto-Bismol[®], Rolaids[®]) for symptomatic relief of heartburn should take GDC-0853 at least 2 hours before or 2 hours after antacid administration because GDC-0853 requires an acidic gastric environment in order to be absorbed.

Patients may be treated with PPIs or H2RAs, but should remain on a stable regimen throughout the study.

At visits with scheduled PK assessments (see Appendix 1), any use of PPIs, H2RAs, and/or *other* antacids (*e.g.*, *Maalox*®, *Pepto-Bismol*®, *Rolaids*®) should be recorded as concomitant medications, including the date and time of last administration.

4.3.2 **Prohibited Therapy**

A listing of concomitant medications that is prohibited or should be used with caution because of potential drug-drug interactions is provided in Appendix 3.

Intravenous, intra-articular, or intramuscular corticosteroids; biologic response modifiers; tofacitinib or other JAK inhibitors; and medications listed below are not allowed during this study and any use will require discontinuation of GDC-0853.

Use of the following therapies is prohibited during the study, unless otherwise specified below:

- Investigational therapy other than study drug
- Abatacept
- Adalimumab
- Anakinra
- Anti-TNF inhibitors (infliximab, etanercept, golimumab, certolizumab, or biosimilar equivalents)
- Chlorambucil
- Cyclophosphamide
- Cyclosporine
- Immunosorbent column
- Intravenous or intramuscular steroids
- Mycophenolate mofetil
- Mycophenolic acid sodium
- Oral anticoagulants, including but not limited to warfarin, dabigatran, rivaroxaban, apixaban
- Anti-platelet agents, e.g. clopidogrel (Note: NSAIDs and low-dose aspirin are acceptable.)
- Heparin, LMWH
- Penicillamine
- Rituximab (or biosimilar equivalent)
- Sirolimus
- Tacrolimus

- Tocilizumab and other anti-IL6R or anti-IL6 agents
- Tofacitinib and other JAK inhibitors
- All biosimilar agents

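### Section 4.3.2 requires GDC-0853 to be stopped after any intra-articular steroid, while Section 4.3.1.1.4 permits up to three such injections from Week 12

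*Combined protocol and SAP*

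**What the plan says.** **Prohibition.** The opening sentence of Section 4.3.2 (Prohibited Therapy) reads "Intravenous, intra-articular, or intramuscular corticosteroids; biologic response modifiers; tofacitinib or other JAK inhibitors; and medications listed below are not allowed during this study" and adds that "any use will require discontinuation of GDC-0853". A second sentence, "Use of the following therapies is prohibited during the study, unless otherwise specified below", then introduces a bullet list whose only steroid entry is "Intravenous or intramuscular steroids". Section 4.5.2 lists use of a medication prohibited under Section 4.3 among the reasons for which study treatment must stop. Such a patient goes to an early termination visit and then 8 weeks of safety follow-up.

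**Permission.** Section 4.3.1.1.4 (Corticosteroids) says "Starting at Week 12 of this study, up to 3 intra-articular corticosteroid injections are permitted". It caps each injection at 40 mg and the yearly total at 80 mg, both in triamcinolone equivalents. The routes it rules out are others: "The use of IV or intramuscular corticosteroids is not permitted in this study".

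**Related text.** Section 3.1 and the synopsis both allow intra-articular steroid for worsening RA throughout the study if the investigator sees fit. Section 3.1 cross-refers to Section 4.3.1.1; the synopsis gives no start week and no limits. Section 4.4.5.1.1 has an injected joint recorded as not done for 12 weeks, after which it may be scored again.

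**The concern.** The same act, one intra-articular injection within the limits after Week 12, is permitted by one section and is a mandatory reason to stop drug under another. Two sites acting in good faith can therefore handle the same kind of patient in opposite ways.

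The primary objective is long-term safety over up to 52 weeks, and the primary efficacy endpoint is ACR50 at Week 52. A patient stopped for a permitted injection contributes less exposure and fewer safety visits and, if he or she would have reached Week 52, no ACR50 assessment at that visit. The discontinuation summary planned in Section 6.2 would partly reflect which section a site had read. Injections are foreseeable, because the protocol itself offers them for worsening disease. Section 6 plans no statistical tests, so the issue is lost and inconsistently handled data, not a biased test.

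**Working it through.** The plan gives no figure on this point to reproduce. The check is first a comparison of texts, then simple arithmetic on the visit schedule.

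**1. Do the rules collide?**

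| Question | Section 4.3.2 (with 4.5.2) | Section 4.3.1.1.4 |
|---|---|---|
| IV or intramuscular steroid | Not allowed; stop drug | Not permitted |
| Intra-articular steroid from Week 12, within limits | Not allowed; any use means stop | Permitted, up to 3 |
| Exception or cross-reference to the other section | None | None |

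The sections agree on the first row and contradict each other on the second.

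**2. Does any wording reconcile them?**
- The exception in "Use of the following therapies is prohibited during the study, unless otherwise specified below" belongs to the sentence that introduces the bullets, not to the sentence before it. Nothing beneath it exempts intra-articular steroid, and the permission stands earlier in the document.
- Section 4.3.1.1 tells investigators to use the procedures that follow it when changing RA medication. This leads to the permission but does not cancel the later stop.
- No precedence rule is stated. A specific rule would normally prevail over a general one, but Section 4.3.2 also names the route explicitly and covers any use.

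**3. Which rule is intended?**
- The bullet "Intravenous or intramuscular steroids" omits intra-articular, so Section 4.3.2 does not match itself.
- Section 4.3.1.1.4 bars only the IV and intramuscular routes.
- A limit of three injections and an annual dose limit have little purpose if the first injection ends treatment.
- Under Section 4.4.5.1.1 an injected joint is scored again after 12 weeks. If drug stopped at the injection, the last visit would be at 8 weeks plus at most 7 days, i.e. 9 weeks, and that rescoring would never be reached.

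Permission appears to be intended.

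**4. Loss per patient if Section 4.3.2 is followed.** Inputs: 52 treatment weeks and 8 weeks of follow-up (Section 3.2.1); visits at Weeks 12, 24, 36 and 52 (Appendix 1); stop at Week 24 without 20% improvement in both joint counts (Section 4.5.2). Assumption: drug stops on the day of the injection. Weeks lost = week in which drug would otherwise have ended − week of injection. End of observation = week of last dose + 8.

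| Injection | Course otherwise | Weeks lost | Share of 52 | Scheduled visits lost | Observation ends |
|---|---|---|---|---|---|
| Week 12 | Completes | 52 − 12 = 40 | 76.9% | 24, 36, 52 | 12 + 8 = Week 20, not 52 + 8 = Week 60 |
| Week 12 | Fails Week 24 check | 24 − 12 = 12 | 23.1% | 24 | Week 20, not 24 + 8 = Week 32 |
| Week 24, check passed | Completes | 52 − 24 = 28 | 53.8% | 36, 52 | 24 + 8 = Week 32, not Week 60 |
| Week 36 | Completes | 52 − 36 = 16 | 30.8% | 52 | 36 + 8 = Week 44, not Week 60 |

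The rows for completers are maxima; stopping for another reason would shorten the loss. In the second row no Week 52 assessment is lost because of the conflict.

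**5. Visit window.** The Week 12 visit is Day 84 ± 4, i.e. Day 80 to 88. For a completer (Day 365): (365 − 80)/7 = 40.7 and (365 − 88)/7 = 39.6 weeks. For a patient who fails at Week 24 (Day 168): (168 − 80)/7 = 12.6 and (168 − 88)/7 = 11.4 weeks. The window moves the Week 12 figures by less than one week.

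**The case against.** The best reply is that the intended reading can be recovered. One word in one sentence is out of line; Section 4.3.1.1.4 is the only place with a start week, a number and dose limits, and Section 3.1 points there. Many sites would follow it or ask the Medical Monitor. A permission also obliges nobody: a site that gives no injection breaks no rule. Both points are fair. They make a literal stop less likely, but they do not remove an explicit instruction to discontinue, which Section 4.5.2 reinforces, and the collision is complete as soon as a permitted injection is given.

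Two further points stand as qualifications. First, a stopped patient is not lost at once: Appendix 1 schedules adverse events, vital signs, ECG and all the ACR components at both the early termination and the safety follow-up visits. What goes is later on-treatment time and, for would-be completers, the Week 52 value. Second, the joint-scoring rule does not say when the injection was given and could also serve joints injected before entry, so it supports the intended reading without proving it.

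Finally, the 40-week figure is a maximum for one hypothetical patient and says nothing about the effect on the whole trial. That is correct, and it is used here only in that sense.

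**Conclusion.** The inconsistency is real and lies in the current protocol text. Read literally, Section 4.3.2 takes patients off GDC-0853 for treatment that Section 4.3.1.1.4 allows. For an injection at Week 12 the cost is 12 weeks in a patient who would fail the Week 24 check and 40 weeks in one who would complete; later injections cost less. These figures assume that drug stops at the injection and that there is no other reason for stopping. The number of patients affected is unknown, because the documents give no injection rate. Since the instruction is a mandatory stop that bears on the primary safety exposure and the Week 52 endpoint, and since correcting it is easy, this should be fixed. Confidence is high.

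A smaller point goes with it: the synopsis allows intra-articular steroid throughout the study, without the Week 12 start or the limits. Section 3.1 has the same looseness, but its cross-reference covers the gap.

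**What to change.** 1. In the opening sentence of Section 4.3.2, add after the steroid routes: *except as permitted in Section 4.3.1.1.4*. The alternative is to delete *intra-articular* from that sentence. The two differ: the exception keeps the mandatory stop for injections before Week 12 or above the limits, whereas deletion leaves no explicit stop for them. The exception is the better choice unless the sponsor wants such injections handled only as protocol deviations; either way the choice should be deliberate.
2. In the synopsis, limit intra-articular steroid to *from Week 12, within the limits of Section 4.3.1.1.4*. Make the same change in Section 3.1 for clarity.

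Section 4.5.2 needs no edit, because it refers back to Section 4.3. The cost is one phrase in Section 4.3.2 and one clause in each of two other places, with no new data or procedures.
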